#### Section 10.5.3.2 Adverse events (AEs)

- Removed irAEs because they are covered by AEs of special interest category in safety summaries.
- Added description of the safety summaries in safety analysis.

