#### **6.2.2 Immune-related adverse events (irAEs)**

The emergence of immune related AE (irAE) may be anticipated based on general experience in clinical studies with similar class of compounds that block the negative immune regulators.

An irAE is a clinically important AE of unknown etiology associated with the study drug exposure. irAEs are typically low grade and self-limited, often occurring after multiple doses, and most frequently involving the GI tract (diarrhea/colitis), skin (rashes), liver (hepatitis), and endocrine systems (a variety of endocrinopathies). Serologic, histologic (tumor sample) and immunological assessments should be performed to verify the immune related nature of the AE, and exclude the neoplastic, infectious or metabolic origin of the AE.

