### **10.5.3 Safety objectives**

#### **10.5.3.1 Analysis set and grouping for the analyses**

For all safety analyses, the safety set will be used. All listings and tables will be presented by treatment group.

The overall observation period will be divided into three mutually exclusive segments:

1. pre-treatment period: from day of patient's informed consent to the day before first dose of study medication
2. on-treatment period: from day of first dose of study medication to 30 days after last dose of study treatment
3. post-treatment period: starting at day 31 after last dose of study treatment.

Safety summaries will primarily be based on all data from the on-treatment period. Following last administration of study treatment, adverse events (including serious adverse events), and new antineoplastic therapies are collected for a period of 150 days for PDR001 treatment and for a period of 30 days for chemotherapy. Following start of new antineoplastic therapy, only study treatment related adverse events will be collected. Select summaries of related adverse events will be produced for the combined on-treatment and post-treatment periods ([Section 10.5.3.2](#)).

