#### **10.5.3.2 Adverse events (AEs)**

Summary tables for adverse events (AEs) have to include only AEs that started or worsened during the on-treatment period, the **treatment-emergent** AEs. However, all safety data (including those from the pre and post-treatment periods) will be listed and those collected during the pre-treatment and post-treatment period are to be flagged.

The incidence of treatment-emergent adverse events (new or worsening from screening/baseline) will be summarized by system organ class and or preferred term, severity (based on CTCAE grades), type of adverse event, relation to study treatment by treatment group.

Deaths reportable as SAEs, and non-fatal serious adverse events will be listed by patient and tabulated by type of adverse event and treatment group.

The following summaries will be produced for the combined on-treatment and post-treatment periods: AEs related to the study treatment by preferred term; SAEs related to the study treatment by preferred term; AEs of special interest related to the study treatment.

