2.8 Safety analysis

Summaries and listings described in this section will be done by study treatment groups based on the Safety set:

- PDR001
- Chemotherapy
- Crossover

For crossover treatment group, summaries will be done if there are more than 10 crossover patients.

The assessment of safety is based on the type and frequency of Adverse Events (AEs) as well as on the number of laboratory values that fall outside of pre-determined ranges (Common Toxicity Criteria for Adverse Events (CTCAE) grading limits or normal ranges as appropriate). Other safety data include electrocardiogram and vital signs.

The overall observation period will be divided into three mutually exclusive segments:

- Pre-treatment period: from day of patient's informed consent to the day before first dose of study treatment,
- On-treatment period: from day of first dose of study treatment to the end of safety follow up, i.e., for PDR001, to 30 days after last dose of PDR001; For chemotherapy, to 30 days after last dose of chemotherapy.

- Post-treatment period: starting at Day 31 after last dose of PDR001 for PDR001 treatment group; Starting at Day 31 after last dose of chemotherapy for chemotherapy treatment group.

If dates are incomplete in a way that clear assignment to pre-, on-, post-treatment period cannot be made, then the respective data will be assigned to the on-treatment period.

Safety summaries will primarily be based on all data from the on-treatment period. Following last administration of PDR001, adverse events (including serious adverse events), and new antineoplastic therapies are collected for a period of 150 days. Following start of new antineoplastic therapy only treatment related adverse events will be collected. Select summaries of related adverse events will be produced for the combined on-treatment and post-treatment periods ([Section 2.8.1](#)).

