- AEs suspected to be study treatment related;
- SAEs related to study treatment

The following listings will be produced:

- All adverse events (safety set)

Deaths (CSR Outputs)

Separate summaries for on-treatment and all deaths (including post-treatment deaths) will be produced by treatment arm, system organ class and preferred term.

All deaths will be listed for the safety set, deaths occurring after the treatment period will be flagged.

EudraCT and clinicaltrials.gov requirements for AEs and Deaths summaries

For the legal requirements of clinicaltrials.gov and EudraCT, two required tables on treatment-emergent adverse events which are not serious adverse events with an incidence greater than 5% and on treatment emergent SAEs and SAEs suspected to be related to study treatment will be provided by SOC and PT on the safety set population. These summaries will include any events starting or worsening in the on-treatment period.

If for a same patient, several consecutive AEs (irrespective of study treatment causality, seriousness and severity) occurred with the same SOC and PT:

- a single occurrence will be counted if there is ≤ 1 day gap between the end date of the preceding AE and the start date of the consecutive AE
- more than one occurrence will be counted if there is > 1 day gap between the end date of the preceding AE and the start date of the consecutive AE

For occurrence, the presence of at least one SAE / SAE suspected to be related to study treatment / non SAE has to be checked in a block e.g., among AE's in a ≤ 1 day gap block, if at least one SAE is occurring, then one occurrence is calculated for that SAE.

The number of deaths resulting from SAEs suspected to be related to study treatment and SAEs irrespective of study treatment relationship will be provided by PT.

Adverse events of special interests / grouping of AEs

An adverse event of special interest is a grouping of adverse events that are of scientific and medical concern specific to compound PDR001. These groupings are defined using MedDRA terms, SMQs (standardized MedDRA queries), HGLTs (high level group terms), HLT (high

[figure not shown]

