level terms) and PTs (preferred terms). Customized SMQs (Novartis MedDRA queries, NMQ) may also be used. A NMQ is a customized group of search terms which defines a medical concept for which there is no official SMQ available or the available SMQ does not completely fit the need. It may include a combination of single terms and/or an existing SMQ, narrow or broad.

For each specified AESI, number and percentage of subjects with at least one event of the AESI occurring during on-treatment period will be summarized.

Summaries of these AESIs will be provided for treatment group PDR001 and Crossover. A listing of all grouping levels down to the MedDRA preferred terms used to define each AESI will be generated.

Summarize adverse events in Crossover treatment group

Patients from randomized to Chemotherapy treatment group are allowed to crossover to PDR001 group after confirmation of PD to chemotherapy. Below diagram specifies how to summarize the AEs for crossover treatment group.

For Scenario 1: do not count AE X (Grade 2) in Period 2 (PDR treatment), as it is an AE starts in Period 1 (Chemotherapy) and resolving during Period 2;

For Scenario 2: count AE X (Grade 2) in Period 2, as this AE starts at least 1 day after previous AE, indicates it is a new AE starts in period 2, not a resolving previous AE;

For Scenario 3: count AE X (Grade 3) in Period 2, as it is a worsening AE

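### The final-CSR summary of adverse events of special interest omits the randomised chemotherapy group, so PDR001 rates have no comparator at that level

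*SAP*

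**What the plan says.** SAP 2.8 sets the general rule for safety outputs: "Summaries and listings described in this section will be done by study treatment groups based on the Safety set". It names three groups (PDR001, Chemotherapy, Crossover) and summarises Crossover only if it has more than 10 patients. Protocol 10.5.3.1 is similar: "All listings and tables will be presented by treatment group".

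Within SAP 2.8.1, the AESI paragraphs define the concept ("An adverse event of special interest is a grouping of adverse events that are of scientific and medical concern specific to compound PDR001"), say that the groupings are built from MedDRA terms and standard or customised queries, and fix the statistic: "For each specified AESI, number and percentage of subjects with at least one event of the AESI occurring during on-treatment period will be summarized". They then name the groups: "Summaries of these AESIs will be provided for treatment group PDR001 and Crossover". Nothing else in the SAP supplies an AESI summary for chemotherapy.

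Protocol 10.5.3.2 lists one AESI output, for the combined on-treatment and post-treatment periods: "AEs of special interest related to the study treatment". It does not say which arms that table covers.

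**The concern.** The trial is randomised, and the design descriptions in Protocol 4.1 and SAP 1.1 speak of efficacy and safety against investigator's choice. The AESI table is the only place where the SAP groups adverse events by medical concept. As background, the Amendment 04 change list gives this reason for dropping a separate immune-related output: "Removed irAEs because they are covered by AEs of special interest category in safety summaries".

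Protocol 6.2.2 describes immune-related events as "most frequently involving the GI tract (diarrhea/colitis), skin (rashes), liver (hepatitis), and endocrine systems", and asks for work-up to exclude neoplastic, infectious or metabolic causes. It therefore accepts that such events can have other origins. If the AESI groupings cover similar events (the SAP does not list them), part of any PDR001 rate may be background. A table with only PDR001-exposed columns cannot show how much.

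**Working it through.** The plan states no AESI rate or AESI precision, so there is no figure to reproduce. The check has four parts.

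**1. Which groups are in the table.** SAP 2.8 lists PDR001, Chemotherapy and Crossover; the AESI paragraph of 2.8.1 lists PDR001 and Crossover. SAP 2.1 defines Crossover as chemotherapy-arm patients later treated with PDR001, so it is not a control. With 10 or fewer crossover patients, PDR001 would be the only column.

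**2. Whether a control column is feasible.** Adverse events are collected throughout treatment in the chemotherapy arm and for at least 30 days after its last dose (Protocol 8.1.1). The groupings are searches on coded terms and can be run on any arm. The AESI statistic uses the on-treatment period, which SAP 2.1.1 defines for every group: to 30 days after last dose, cut for chemotherapy patients at the start of crossover PDR001. The longer 150-day collection after PDR001 does not affect an on-treatment table.

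**3. Whether preferred-term rows can stand in.** SAP 2.8.1 counts a patient once in each preferred-term row, whereas an AESI counts a patient once across all its terms. With term counts n_j in N patients, the table fixes only these bounds:

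max(n_j)/N ≤ AESI rate ≤ sum(n_j)/N

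For assumed counts of 2, 2, 1 and 1 with N = 40, the bounds are 2/40 = 5% (full overlap) and (2+2+1+1)/40 = 6/40 = 15% (no overlap).

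**4. What the added column could show.** Protocol Amendment 06 (study status) gives 122 randomised, 82 of them to PDR001, so 122 − 82 = 40 to chemotherapy. The Safety Set may be smaller. All event rates below are assumptions.

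Exact (Clopper-Pearson) 95% intervals for a chemotherapy AESI rate with N = 40:

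- 0/40 = 0%: 0 to 8.8%
- 2/40 = 5%: 0.6 to 16.9%
- 4/40 = 10%: 2.8 to 23.7%
- 8/40 = 20%: 9.1 to 35.6%

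Difference from an assumed PDR001 rate of 30%, with SE = sqrt(p1(1−p1)/82 + p0(1−p0)/40) and Wald 95% limits at ±1.96 SE:

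- p0 = 5%: SE = sqrt(0.21/82 + 0.0475/40) = 0.061; +25 points (13 to 37)
- p0 = 10%: SE = sqrt(0.21/82 + 0.09/40) = 0.069; +20 points (6 to 34)
- p0 = 20%: SE = sqrt(0.21/82 + 0.16/40) = 0.081; +10 points (−6 to 26)

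The table as planned would show the same 30% in all three cases. The intervals are wide, so the column would be informative but not decisive.

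**The case against.** A reader might infer that immune-type toxicity has no control rate at all, or that the main harm of interest loses its randomised comparison. The documents do not support that. Under SAP 2.8 and 2.8.1, chemotherapy is a column in the on-treatment tables by system organ class and preferred term, and in those for serious events, discontinuation, interruption and fatal outcome. All adverse events are listed. SAP 2.8.2 adds biochemistry shift tables, and its Table 2-4 includes AST, ALT and bilirubin, although the final choice of parameters is left to the table shells.

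A reader might also infer an undeclared departure from the protocol, because SAP section 4 mentions only COVID-19. That is doubtful:

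- SAP 2.1 leaves the grouping details to each subsection, and the AESI definition ties the concept to PDR001.
- Presenting tables by treatment group does not oblige every table to hold every group. Protocol 10.5.3.4 itself confines ECG outputs to the PDR001 arm.
- The only AESI table that the protocol names covers related events over the combined periods, not an on-treatment table with a control column.
- The safety objective in Protocol Table 3-1 is to characterise PDR001, without a comparator.

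Three further points stand. This SAP serves the final report, and the interim report that preceded it may already have tabulated chemotherapy AESIs; the documents do not show it. Ascertainment may differ, because the immunological work-up of suspected immune-related events sits in the PDR001-arm section (Protocol 6.2), and the visit schedules list such events for PDR001 and crossover but only adverse events for chemotherapy. Crude percentages may mislead where exposure differs.

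None of this supplies an AESI-level control rate in the final report. The differences in exposure and work-up call for a caveat on the column, not for leaving it out.

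**Conclusion.** The point holds in a limited form. The on-treatment AESI summary planned for the final report has no chemotherapy column, and the remaining outputs do not allow a per-patient AESI rate to be read off for that group, although one could be derived ad hoc from the listing. Single preferred terms and laboratory shifts keep their control rates.

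This is a worthwhile, inexpensive improvement, not a clear protocol breach. It concerns at most 40 patients. The effect on interpretation cannot be sized, because no AESI rates are given; the percentages in the working are assumptions, apart from the arm sizes. The conclusion also assumes that the unlisted AESI groupings contain events that can occur on chemotherapy or from the disease.

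**What to change.** Reword the group sentence in SAP 2.8.1 along these lines:

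> AESI summaries will be presented for the PDR001, Chemotherapy and Crossover groups (Crossover only with more than 10 patients), applying identical MedDRA groupings and the on-treatment period that Section 2.1.1 defines for each group.

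The reference to each group's own period matters, because the chemotherapy window is cut at crossover; a single common window would contradict SAP 2.1.1.

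Add a footnote that the comparison is descriptive and that exposure and the work-up of suspected immune-related events may differ between arms, or give exposure-adjusted rates beside the percentages. SAP 2.5.1 already derives duration of exposure for both treatments.

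The cost is one sentence, one table column and a footnote, with no new data collection.

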2.8.2 Laboratory data

Laboratory data will be converted into SI units and classified (by Novartis statistical programming) into CTC grades according to CTCAE. Grade 5 will not be used.

A Grade 0 CTC grade will be set when laboratory value is:

- Within LLN and ULN and grading in both direction,
- Below ULN and grading in hyper direction,
- Above LLN and grading in hypo direction.

Laboratory data for which a CTC grading does not exist will be classified into low, normal, or high based on local laboratory normal ranges as applicable. For the laboratory parameters where the CTC grades depend on the normal ranges, when normal ranges are captured as 0 and 888888.xxx or above then the normal ranges and normal ranges indicator should not be present and the corresponding CTC grade should not be derived.

The following summaries will be produced for hematology and biochemistry parameters:

- For parameters with CTC grades: Shifts from baseline to the worst post-baseline CTC grade,
- For parameters with no CTC grades defined: Shifts from baseline to the worst post-baseline using low/normal/high classifications,

The following listings will be produced:

- Listing of patients with laboratory abnormalities of CTC grade 3 and 4

Table 2-4 and Table 2-5 list all laboratory parameters with CTCAE or normal ranges that have been collected in the study. The laboratory parameters that will be summarized in the CSR will be mentioned in the TLF shells document. Other laboratory parameters without confirmed normal ranges include:

EBV test, DNA levels in plasma: ‘Copies/mL’ will be reported units. EBV conversion factor: Copies/mL = $10^{\log \text{IU/mL} / 0.369}$.

Serology exam of Anti-DNA antibodies (Abs), Anti-nuclear abs, Anti-phospholipid abs, Anti-mitochondrial abs.

Table 2-4 Laboratory parameters for which CTCAE grades are defined

Hematology and coagulation		Biochemistry	
White Blood Cells (WBC)	↑ ↓	Creatinine	↑
Hemoglobin	↓	Sodium	↑↓
Platelets counts	↓	Potassium	↑↓
Absolute Neutrophils	↓	Corrected Calcium	↑↓
Absolute Lymphocytes	↑ ↓	Magnesium	↑↓
APTT	↑	Albumin	↓
INR	↑	AST (SGOT)	↑
		ALT (SGPT)	↑
		Total Bilirubin	↑
		Inorganic Phosphate	↓
		Glucose (fasting)	↑↓
		Glucose, plasma (fasting)	↑↓
		Alkaline Phosphatase	↑

↑ Indicates that CTC grade increases as the parameter increases.

↓ Indicates that CTC grade increases as the parameter decreases.

Table 2-5 Laboratory parameters (without CTCAE grades) for which lab reference ranges are defined

Hematology and coagulation	Biochemistry	Serology
Prothrombin time (PT)	Blood urea nitrogen (BUN)	c-Reactive protein (CRP)
Absolute Basophils	Urea*	Rheumatoid factor (RF)
Absolute Eosinophils	TSH	
Absolute Monocytes	Total T4	
	Direct bilirubin	
	Indirect bilirubin	
	Calcium	
	Chloride	
	Bicarbonate	

*Urea will be converted to BUN and reported as BUN

Imputation rules

CTC grading for blood differentials is based on absolute values.

If laboratory values are provided as ‘<X’ (i.e. below limit of detection) or ‘>X’, prior to conversion of laboratory values to SI unit, these numeric values are set to X.

The following rules will be applied to derive the WBC differential counts when only percentages are available for a xxx differential

$$\text{xxx count} = (\text{WBC count}) * (\text{xxx \%value} / 100)$$

Corrected calcium can be derived using the reported total calcium value and albumin at the same assessment using the following formula:

$$\text{Corrected Calcium (mg/dL)} = \text{Calcium (mg/dL)} - 0.8 [\text{Albumin (g/dL)} - 4]$$

In order to apply the above formula, albumin values in g/L will be converted to g/dL by multiplying by 0.1), calcium values in mmol/L will be converted to mg/dL by dividing by 0.2495. For calculation of laboratory CTC grades 0 and 1, the normal range for derived corrected calcium is set to the same limits (in mg/dL) as for calcium.

CTC grades for the derived absolute WBC differential counts (neutrophils, lymphocytes) and corrected calcium are as defined in the previous section.

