**Table 7-6 Local/central clinical laboratory parameters collection plan**

Test Category	Test Name
Hematology	Hematocrit, Hemoglobin, Platelets, White blood cells with Differential (Basophils, Eosinophils, Lymphocytes, Monocytes, Neutrophils)
Chemistry	Albumin, Alkaline phosphatase, ALT (SGPT), AST (SGOT), Bicarbonate, Calcium, Chloride, Sodium, Potassium, Creatinine, Glucose (fasting) Magnesium, Inorganic Phosphate, Total Bilirubin (also measure direct and indirect bilirubin if total bilirubin is > grade 1), Blood Urea Nitrogen (BUN) or Urea
Coagulation	Prothrombin time (PT) or International Normalized Ratio (INR), Activated partial thromboplastin time (APTT)
Thyroid	Free T4, TSH (Thyroid Stimulation Hormone)
Cytokines 	Interferon-gamma (IFN- $\gamma$ ), Interleukin-6 (IL-6), Interleukin-1 (IL-1), Tumor necrosis factor-alpha (TNF- $\alpha$ )
EBV 	DNA levels in plasma
Serology exam in serum 	Anti-DNA antibodies (Abs), Anti-nuclear abs, Anti-phospholipid abs, Anti-mitochondrial abs, c-Reactive protein (CRP), Rheumatoid factor (RF)
Pregnancy	Serum and/or urine samples only for women of childbearing potential
 To be performed at Screening/Baseline for all patients, and ad hoc (by ELISA), if cytokine release syndrome is suspected only for patients in PDR001 arm.  To be performed by a Central laboratory.  To be terminated upon implementation of Protocol Amendment 05.  To be terminated upon implementation of Protocol Amendment 06.	

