2.10.5 Data analysis of biomarkers

Basic analysis and reporting are specified in [Table 2-10](#).

Percent change is calculated as $((\text{visit } i - \text{baseline})/\text{baseline}) * 100$.

Fold change is calculated as $\text{visit } i / \text{baseline}$.

Table 2-10 Reporting of analysis

Biomarker	Report
Immune-related genes, including PD-L1, CD8, LAG-3 and TIM-3 from tumor sample	Listing of biomarkers, including demographic variables, collect time point, levels and clinical endpoints.
	Summary table: levels at each time point (baseline and post-baseline) and change/percent change/fold change from baseline at each time point. Descriptive statistics include N, mean, standard deviation, % CV, median, minimum and maximum. For fold change, geometric mean and geometric % CV will also be included.
	Summary tables: PFS will be summarized for subjects with a. PD-L1 high (PD-L1 $\geq 50\%$)/mid (PD-L1 1% - 50%)/low (PD-L1 $< 1\%$) expression at baseline and b. CD8 $< 1\%$ CD8 $\geq 1\%$ expression at baseline using the Kaplan-Meier (KM) method. Median PFS, with corresponding 90 CI, and 25 th and 75 th percentiles (Brookmeyer and Crowley 1982 , Klein and Moeschberger 1997) will be presented. KM estimates for PFS proportions at specific timepoints, along with 95% CI (Greenwood's formula , Kalbfleisch and Prentice 2002) will also be provided.
Cytokine analysis markers, including but not limited to IFN- γ , TNF- α , IL-6 from blood sample	Summary table: levels at each time point (baseline and post-baseline) and change/percent change/fold change from baseline at each time point. Descriptive statistics include N, mean, standard deviation, % CV, median, minimum and maximum. For fold change, geometric mean and geometric % CV will also be included.
	Listing of biomarkers, including demographic variables, collect time point, levels and clinical endpoints.

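### SAP 2.8.2, in the text supplied, puts 0.369 inside the exponent of the EBV DNA conversion, which makes it a power law and not a unit conversion (minor; check against the source)

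*SAP*

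**What the plan says.** Protocol Table 7-6 lists EBV "DNA levels in plasma" as a central-laboratory test. Table 7-1 schedules it at screening, on Day 1 of Cycles 1 to 3, every 12 weeks after that and at end of treatment. Table 7-3 schedules it again for crossover patients.

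SAP section 2.8.2 introduces EBV under the words "Other laboratory parameters without confirmed normal ranges include", sets copies/mL as the reporting unit and gives the rule "EBV conversion factor: Copies/mL = $10^{\log \text{IU/mL} / 0.369". In the text supplied, the exponent ends after 0.369. The base of the logarithm is not stated and there is no worked value.

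Whether EBV is tabulated at all is left to another document: "The laboratory parameters that will be summarized in the CSR will be mentioned in the TLF shells document".

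**The concern.** The SAP labels the rule an "EBV conversion factor". A factor that changes units multiplies or divides a concentration, so doubling the IU/mL must double the copies/mL. With 0.369 in the exponent that property is lost. As printed, 1 IU/mL converts to exactly 1 copy/mL whatever constant is used, so 0.369 does not act as a factor.

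The other unit conversions in section 2.8.2 are proportional: albumin is multiplied by 0.1 and calcium is divided by 0.2495. The EBV line is the exception.

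At stake is the reported viral load in a disease that the protocol's background section describes as EBV-associated. SAP section 1 says the plan may also serve as a reference for outputs beyond the study report, such as abstracts and manuscripts, so a wrong line could be carried further than one listing.

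**Working it through.** **Inputs.** The constant 0.369 and the printed form come from SAP 2.8.2. Two inputs are assumptions. The logarithm is taken as base 10 because it is paired with a power of 10. The EBV levels are an illustrative range, since the documents give none. The plan states no converted value that could be reproduced.

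**Formulas**, with x the level in IU/mL:

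- As printed: 10^(log10(x) / 0.369) = x^(1/0.369) = x^2.710.
- Factor outside the exponent: 10^(log10 x) / 0.369 = x / 0.369 = 2.710x.
- Ratio of the two: x^2.710 / 2.710x = 0.369 × x^1.710.

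| Assumed IU/mL | As printed | Factor outside | Ratio |
|---|---|---|---|
| 1 | 1 | 2.71 | 0.369 |
| 10 | 513 | 27.1 | 19 |
| 100 | 263,060 | 271 | 971 |
| 1,000 | 1.35 × 10^8 | 2,710 | about 49,800 |
| 10,000 | 6.92 × 10^10 | 27,100 | about 2.55 million |
| 100,000 | 3.55 × 10^13 | 271,000 | about 131 million |

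**Where the direction turns.** The ratio is 1 when x^1.710 = 1/0.369, that is, at x = 1.79 IU/mL. Below that level the printed rule gives too small a value.

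**Effect on a change.** If EBV changes by a multiple m, the printed rule reports m^2.710. So 2 becomes 6.5, 10 becomes 513, and a fall to one tenth becomes a fall to 0.0019. With the factor outside, m is unchanged.

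**Log base.** With a natural logarithm the printed rule becomes x^(2.303/0.369) = x^6.24, which gives about 1.74 million at 10 IU/mL. Moving the factor outside would not repair this, because 10^(ln x) = x^2.303. The base therefore has to be stated in either case.

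**Direction of the factor.** Dividing and multiplying by 0.369 differ by 1/0.369² = 7.3-fold. The documents do not show which one the assay requires.

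**The case against.** **The error may lie in the extraction.** The point turns on where one superscript ends, and a program read that from a PDF. If the original superscript closes before the division, the line is already IU/mL divided by 0.369 and only the unstated log base remains. The supplied text shows displaced elements elsewhere: in Protocol 14.3.1.1 a connecting word sits at the front of the baseline-hazard formula. The label conversion factor also suggests that a proportional rule was meant. This objection stands, and it is why the point is conditional.

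**The fold-change reading.** A reader might infer that every fold change in the plan is distorted. The documents do not support that. SAP 2.10.5 defines the quantity ("Fold change is calculated as $\text{visit } i / \text{baseline"), but Table 2-10 applies it to "Immune-related genes, including PD-L1, CD8, LAG-3 and TIM-3 from tumor sample" and to "Cytokine analysis markers, including but not limited to IFN- γ , TNF- α , IL-6 from blood sample". EBV DNA is in neither row. The laboratory summaries named in 2.8.2 are shift tables for hematology and biochemistry and a listing of grade 3 and 4 abnormalities. EBV is in neither Table 2-4 nor Table 2-5. An EBV analysis could sit in the output shells or in blacked-out text, but none is visible.

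**The efficacy reading.** A reader might also infer that efficacy conclusions are at risk. No visible objective or endpoint in Protocol Table 3-1 or SAP Table 1-1 uses EBV DNA.

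**Another document governs the programming.** SAP section 1 places derived-variable specifications in a separate programming document that is not available here, so the code may be right even if this line is not. Values near 10^10 copies/mL would also probably be noticed. Both are fair points. They lower the risk without making the printed rule a conversion.

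**The size depends on assumed levels.** This also stands. An inflation of hundreds to millions of times describes only part of the range. At 10 IU/mL it is 19-fold, and below 1.8 IU/mL the sign reverses.

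**Conclusion.** On the text supplied, the rule is (IU/mL)^2.71 and not a unit conversion. Any EBV level, or change in level, derived from it would be wrong by an amount that grows with the level, from about 19-fold at 10 IU/mL to about 2.6 million-fold at 10,000 IU/mL.

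This rests on three assumptions: base-10 logarithms, the chosen EBV levels, and a superscript that has been read correctly. The comparison also takes division by 0.369 as the intended direction, which the documents do not confirm.

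The severity is minor. What is affected is the reporting unit of a laboratory value that feeds no visible primary or secondary endpoint and no visible planned fold change.

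**What to change.** 1. Check the superscript in the original SAP and the derivation in the programming specification.
2. If 0.369 is in the exponent, replace the line with Copies/mL = 10^(log10 IU/mL) / 0.369, after the central laboratory has confirmed that the factor divides and does not multiply.
3. In either case, state the log base and add one worked value. If division is confirmed, 1,000 IU/mL gives 2,710 copies/mL.
4. Re-derive any EBV output already programmed from the printed line.

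The cost is one line of SAP text and one line of code, plus a rerun of any affected EBV output. SAP section 1 allows corrections without amendment only for minor formatting or spelling in the output shells. A changed derivation therefore belongs in an amendment before database lock or an addendum after it.
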